6.3.1.2 Questionnaires

The ARCI MBG and PCAG scales will be administered as scheduled in [Table 1](#).

The 49-item ARCI is a shortened version (49 true-false items) compiled by Martin et al. ³⁷ from the 550-item Addiction Research Center Inventory (ARCI) originally developed by Haertzen. ^{38,39} This version contains 5 scales, which measure the following effects: Euphoria -- Morphine-Benzedrine Group (MBG) scale; Stimulant effects -- Amphetamine (A) scale and Benzedrine Group (BG) scale; Dysphoria -- Lysergic Acid Diethylamide (LSD) scale; and Sedation -- Pentobarbital-Chlorpromazine-Alcohol Group (PCAG) scale. Subjects indicate their responses by selecting “False” or “True.” One point is given for each response that agrees with the scoring direction on the scale (i.e., True items receive a score of 1 if the answer is “True;” no points are given when the answer is opposite to the scoring direction).

The following 2 scales will be administered:

- Pentobarbital Chlorpromazine Alcohol Group – PCAG
- Morphine Benzedrine Group – MBG

The items pertaining to the ARCI MBG and ARCI PCAG scales are presented below:

Questions Contributing to ARCI MBG & PCAG Scales	Scale
	PCAG MBG
1. My speech is slurred.	T
2. I am not as active as usual.	T
3. I have a feeling of just dragging along rather than coasting.	T
4. I feel sluggish.	T
5. My head feels heavy.	T
6. I feel like avoiding people, although I usually do not feel this way.	T
7. I feel dizzy.	T
8. It seems harder than usual to move around.	T
9. I am moody.	T
10. People might say that I am a little dull today.	T
11. I feel drowsy.	T
12. I am full of energy.	F
13. Today I say things in the easiest possible way.	T
14. Things around me seem more pleasing than usual.	T
15. I have a pleasant feeling in my stomach.	T
16. I feel I will lose the contentment that I have now.	T

17. I feel in complete harmony with the world and those about me.	T
18. I can completely appreciate what others are saying when I am in this mood.	T
19. I would be happy all the time if I felt as I feel now.	T
20. I feel so good that I know other people can tell it.	T
21. I feel as if something pleasant had just happened to me.	T
22. I would be happy all the time if I felt as I do now.	T
23. I feel more clear-headed than dreamy.	F T
24. I feel as if I would be more popular with people today.	T
25. I feel a very pleasant emptiness.	T
26. My thoughts come more easily than usual.	T
27. I feel less discouraged than usual.	T
28. I am in the mood to talk about the feelings I have.	T
29. I feel more excited than dreamy.	F
30. A thrill has gone through me one or more times since I started this test.	F

T = True item

F = False item

Responses to individual items will be included. If one of the individual items is missing, the associated scale(s) score will not be calculated.

6.3.2 Modified Observer's Assessment of Alertness/Sedation (MOAA/S)

The MOAA/S is an observer-rated measure of alertness/sedation that is used widely in clinical research. It is based on the following 6 items, rated on a scale from 5 (not sedated) to 0 (unarousable):

The Observer's Assessment of Alertness/Sedation Scale (OAA/S) was developed to measure the level of alertness in subjects who are sedated.³⁶ The OAA/S is a reliable validated measure and was shown to be sensitive to different levels of sedation and is composed of 4 assessment categories that include responsiveness, speech, facial expression, and eyes. The Modified Observer's Assessment of Alertness/Sedation Scale (MOAA/S) includes only the Responsiveness assessment category. It is easy and quick to administer (less than 1 minute). The subjects' level of responsiveness is measured in a 5-point Likert scale:

Responsiveness	Score
Responds readily to name spoken in normal tone	5 (Alert)
Lethargic response to name spoken in normal tone	4
Responds only after name is called loudly and/or repeatedly	3
Responds only after mild prodding or shaking	2
Does not respond to mild prodding or shaking	1 (Deep Sleep)

7 ADVERSE EVENTS DOCUMENTATION

7.1 Definitions

An AE is defined as any untoward medical occurrence in a subject administered an investigational product and which does not necessarily have a causal relationship with the treatment. An AE can therefore be any unfavorable and unintended sign (including a clinically significant abnormal clinical laboratory finding, for example), symptom, or disease temporally associated with the use of an investigational product, whether or not related to the investigational product.

A suspected adverse reaction (SAR) is any AE for which there is a reasonable possibility the drug caused the AE. 'Reasonable possibility' means there is evidence to suggest a causal relationship between the drug and the AE. A suspected adverse reaction implies a lesser degree of certainty about causality than adverse reaction, which means any AE caused by a drug.

Regarding marketed medicinal products, an adverse drug reaction is defined as a response to a drug which is noxious and unintended and which occurs at doses normally used in man for prophylaxis, diagnosis, or therapy of disease or for modification of physiological function.

An AE may be:

- A new illness,
- Worsening of a concomitant illness,
- An effect of the study drug including comparator; it could be an abnormal clinical laboratory value as well as a significant shift from baseline within normal range which an investigator considers to be clinically important.

Surgical procedures themselves are not AEs. They are therapeutic measures for conditions that required surgery. The condition for which the surgery is required is an AE, if it occurs or is detected during the study period. Planned surgical measures permitted by the clinical study protocol and the condition(s) leading to these measures are not AEs, if the condition(s) was (were) known before the start of study treatment. In the latter case, the condition should be reported as medical history.

An SAE or reaction is any untoward medical occurrence that at any dose:

- Results in death,
- Is life-threatening,
- Requires inpatient hospitalization or prolongation of existing hospitalization,
- Results in persistent or significant disability or incapacity (defined as a substantial disruption of a person's ability to conduct normal life functions),
- Is a congenital anomaly or birth defect,
- Is an important medical event (including development of drug dependence or drug abuse) that may jeopardize the subject or may require intervention to prevent one of the other outcomes listed above (according to medical judgment of an investigator).

7.2 Severity Assessment

All AEs will be graded as mild, moderate, or severe according to the following definitions:

Mild: Causing no limitation of usual activities; the subject may experience transient slight discomfort.

Moderate: Causing some limitation of usual activities; the subject may experience annoying discomfort.

Severe: Causing inability to carry out usual activities; the subject may experience intolerable discomfort or pain.

Every effort will be made to obtain an adequate evaluation of the severity.

7.3 Causality Assessment

An investigator will determine the relationship of any AE to the study drug using the guidelines presented in [Table 6](#).

Table 6. Adverse Event Relationship to Study Drug

Relationship to Drug	Comment
Reasonable Possibility	
A temporal relationship exists between the AE onset and administration of the investigational product that cannot be readily explained by the subject's clinical state or concomitant therapies.
 
Furthermore, the AE appears with some degree of certainty to be related, based on the known therapeutic and pharmacologic actions or AE profile of the investigational product.
 
In case of cessation or reduction of the dose the AE may abate or resolve and it may reappear upon rechallenge.

No Reasonable Possibility	
Evidence exists that the AE has an etiology other than the investigational product.
 
For SAEs, an alternative causality must be provided (e.g., preexisting condition, underlying disease, intercurrent illness, or concomitant medication).

7.4 Adverse Event Monitoring

For the purposes of this study, the monitoring period for AEs extends from the time of first study treatment administration in the Qualification phase until Day 14 of the Treatment phase. Any medical conditions occurring from the time of signing informed consent until the first dose of study treatment in the Qualification phase will be recorded as medical history. If the condition meets the criteria for an SAE it will be reported as described in section [7.6](#).

Subjects will be questioned on their health status prior to each study treatment and periodically thereafter, including prior to PD measurements. Open-ended questions will be asked.

During the study, all AEs spontaneously reported by the subject, observed by the clinical staff or elicited by general questioning will be recorded for all subjects and reported in the CRF.

Every effort will be made to obtain an adequate follow-up of the subjects and the final outcome. Should any subject choose to withdraw from the study, they will be advised of the safety precautions to be taken.

Any AE which remains unresolved as of the last visit will require an appropriate evaluation and follow-up until the AE has been resolved or a reasonable explanation for its persistence found, or is deemed mild and safely resolving.

It is an investigator's responsibility to ensure subjects experiencing adverse events receive appropriate follow-up, treatment where required, and that every action is well-documented.

Classification of AEs will be performed by system organ class (SOC) and preferred term (PT) using the Medical Dictionary for Regulatory Activities (MedDRA), version 22.0 or higher.

Concomitant medications will be coded using the World Health Organization Drug Dictionary-Enhanced (WHO-DDE March 2019 or later).

7.5 Reporting of Pregnancy

Pregnancy in a female study subject shall be reported to the sponsor within 24 hours of the knowledge of its occurrence by an investigator or delegate (for pregnancies occurring during the course of the study or up to 30 days following the end of the study). Because of the possibility the fetus/embryo could have been exposed to the study drug through the parent and for the subject's safety, the pregnancy will be followed up to determine its outcome, including spontaneous or voluntary termination, details of birth, presence or absence of any birth defects, congenital anomalies, or maternal and/or newborn complications.

The pregnancy will be recorded and reported by the clinical site to the sponsor. Pregnancy follow-up will also be properly recorded to ensure quality and completeness of the data belonging to the study drug and will include an assessment of the possible causal relation between the study drug and any pregnancy outcome. Any SAE experienced during pregnancy will be reported on an SAE Report Form.

7.6 Serious Adverse Event Reporting

The CRU will notify any SAE to the sponsor or designee, without regard to causality, within 24 hours after becoming aware of its occurrence.

If, during follow-up, any non-serious AE worsens and eventually meets the criteria for an SAE, that AE should be recorded as a new SAE.

The initial SAE report must be as complete as possible, including details of any current illness and SAE, and an assessment of the causal relationship between the event and the investigational product(s). Information not available at the time of the initial report (e.g., an end date for the AE, laboratory values received after the report, or hospital discharge summary) must be documented. All follow-up information must be reported as soon as the relevant info is available, in the same manner as the initial report.

If an SAE occurs to a subject during this study, the SAE report and relevant medical records should be faxed at the time of the report to Arbor Safety Inbox [REDACTED] or scanned and emailed [REDACTED]. The SAE may also be reported by telephone to Arbor Drug Safety [REDACTED].

An SAE will be considered "unexpected" if the AE is not listed in the US product inserts (USPIs) or is not listed at the specificity or severity that has been observed; or, if an investigator brochure is not required or available, is not consistent with the risk information described in the general investigational plan or elsewhere in the current application. "Unexpected," as used in this definition, also refers to AEs that are mentioned in the USPIs as occurring with a class of drugs or as anticipated from the pharmacological properties of the drug, but are not specifically mentioned as occurring with the particular drug under investigation.

The CRU will determine whether any serious, unexpected, related AE must be reported to the institutional review board (IRB). If so, the event will be reported via fax or email within 15 calendar days of an investigator or staff becoming aware of the event.

The sponsor will determine whether the SAE must be reported in an expedited manner to the applicable regulatory agencies. If so, the sponsor will report the event to those agencies and to all participating investigators.

If reports of any new and unexpected AEs become available to the sponsor during the clinical portion of this study, the sponsor will advise the CRU, through its clinical investigator, of those events. If required, the sponsor will report to the applicable regulatory authorities.

8 DATA ANALYSIS AND STATISTICAL METHODS

8.1 Analysis Populations

8.1.1 Qualification Phase

8.1.1.1 Qualification Randomized Population

The Qualification Randomized population will include all subjects who are assigned a randomization number in the Qualification phase.

8.1.1.2 Qualification Safety Population

The Qualification Safety population will include all subjects who are randomized into the Qualification phase and receive at least 1 dose of either the study drug or placebo.

8.1.2 Treatment Phase

8.1.2.1 Randomized Population

The Randomized population will include all subjects who are assigned a randomization number in the Treatment phase.

8.1.2.2 Safety Population

The Safety population will include all subjects who are randomized into the Treatment phase and receive at least 1 dose of 1 of the study drugs or placebo.

8.1.2.3 Completer Population

All subjects in the Safety population who complete all 5 crossover periods in the Treatment phase of the study, and have sufficient data for evaluation of the primary endpoint (based on a blinded review of data prior to database lock) will be included in the Completer population. Subjects who do not have at least 1 observation within 2 hours of T_{max} for each treatment for Drug Liking VAS will be excluded from the Completer population.

8.1.2.4 Modified Completer Population

All subjects in the Completer population, excluding problematic subjects with unreliable responses which can alter study results, will be included in the Modified Completer population. For the Drug Liking VAS scale, the following elimination criteria will be used to define the Modified Completer population.

- a) Similar E_{max} scores (within a 5-point difference) for a subject across all study treatments (including placebo)

OR

b) E_{max} for placebo > 60 AND the $E_{max}(\text{placebo}) - E_{max}(\text{positive control}) \geq 5$

Criterion a) and b) will be applied to the Drug Liking VAS data on the Completer population. If no subjects are excluded when these criteria are applied, then the Modified Completer population is the same as the Completer population.

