8.5 Pharmacodynamics

8.5.1 Pharmacodynamic Endpoints

Pharmacodynamic endpoints will be evaluated as described in [Table 7](#) and all PD data will be analyzed using the Modified Completer population.

Table 7. Pharmacodynamic Endpoints

Description	Type	Endpoints
Drug Liking	Bipolar VAS	E_{max} , E_{min} , TE_{max} , TE_{min} , and TA_AUE
Overall Drug Liking	Bipolar VAS	E_{max}
Take Drug Again	Bipolar VAS	E_{max}
High	Unipolar VAS	E_{max} , TE_{max} , and TA_AUE
Good Effects	Unipolar VAS	E_{max} , TE_{max} , and TA_AUE
Bad Effects	Unipolar VAS	E_{max} , TE_{max} , and TA_AUE
Any Effects	Unipolar VAS	E_{max} , TE_{max} , and TA_AUE
Feeling Drunk	Unipolar VAS	E_{max} , TE_{max} , and TA_AUE
Drowsiness/Alertness	Bipolar VAS	E_{min} , TE_{min} , and TA_AOE
Relaxation/Agitation	Bipolar VAS	E_{min} , TE_{min} , and TA_AOE
Addiction Research Center Inventory (ARCI) Morphine- Benzedrine Group (MBG) Scale	Questionnaire score	E_{max} , TE_{max} , and TA_AUE
ACRI Pentobarbital- Chlorpromazine-Alcohol Group (PCAG) Scale	Questionnaire score	E_{max} , TE_{max} , and TA_AUE
Modified Observer's Assessment of Alertness/Sedation (MOAA/S)	Observer's score	E_{min} , CFB_{min} , and TA_AOE

CFB_{min} = change from baseline to minimum effect, E_{max} = maximum (peak) effect, E_{min} =minimum effect, TA_AOE= time-averaged area over the effect-time curve, TA_AUE=time-averaged area under the effect-time curve, TE_{max} =time of maximum (peak) effect, TE_{min} =time of minimum effect, VAS=Visual Analog Scale

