8.5.2.2 Secondary Analysis

Although a margin of 15 has been selected for Hypothesis 1 for consistency with the Qualification phase criteria, subjects may have lower responses with alprazolam and higher responses with placebo in the Treatment phase as compared to the Qualification phase,^{19,31} particularly for lower abuse potential drugs such as benzodiazepines (i.e., Schedule IV drugs). Therefore, in the case that the difference between the active control and placebo does not meet

the pre-specified criteria for validity of at least 15 points, secondary analysis will be performed. Details of the secondary analysis will be described in the SAP.

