8.9 Determination of Sample Size

As reported in an unpublished HAP study evaluating doses of 1.5 mg and 3.0 mg of alprazolam, the mean paired difference (SD) for Drug Liking VAS E_{max} VAS between alprazolam 1.5 mg and placebo was 26.3 (18.62). For alprazolam 3.0 mg vs. placebo, the mean difference (SD) was 26.6 (17.83). A margin of 15, with a correlation of 0, and an upper-tailed test with a significance level of 0.05 results in 48 completers for the comparison of alprazolam 1.5 mg vs. placebo, and 42 completers for the comparison alprazolam 3.0 mg vs. placebo. The more conservative sample size estimate of 48 subjects will be used.

Assuming a drop-out rate of approximately 25%, and allowing for missed data and problematic subjects as defined for the Modified Completer population, approximately 60 subjects are planned for randomization into the Treatment phase in order to achieve a minimum of 48 completers (at least 4 subjects per 10 treatment sequences).

Due to potential sedative effects that may prevent subjects from completing measures and expected natural attrition, replacement subjects may be considered in order to meet the minimum number of completers, in the event that the preplanned attrition rate of 25% is surpassed.

Subjects will be consecutively randomized into the Qualification phase until the target number of 60 subjects eligible for participation in the Treatment phase is reached.

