## 7.4 Analysis of Pharmacodynamics Measures

The primary analysis of PD data will be analyzed for the Modified Completer population.

$E_{max}$  of Drug Liking, Overall Drug Liking, Take Drug Again and High VAS from the qualification phase will be summarized by treatment and paired difference for the Modified Completer population using standard descriptive statistics. The data will be evaluated to confirm that an appropriate population was selected for the treatment phase.

During the treatment phase, PD measures at each time point will be summarized by treatment using descriptive statistics and presented graphically. Derived endpoints will be summarized by treatment and paired difference using descriptive statistics. Only descriptive statistics will be output for  $TE_{max}$  and  $TE_{min}$ . Descriptive statistics will include n, mean, standard error (SE), minimum, first quartile (Q1), median, third quartile (Q3) and maximum for all PD values and endpoints other than  $TE_{max}$  and  $TE_{min}$ . For  $TE_{max}$  and  $TE_{min}$ , minimum, Q1, median, Q3 and maximum will be output.

A mixed-effects model for a crossover study design will be used to compare the primary and secondary PD endpoints between treatments (e.g.,  $E_{max}$ ,  $E_{min}$ ,  $CFB_{min}$ ,  $TA\_AUE$  and  $TA\_AOE$ ) with appropriate covariance-variance structure, if the residuals are normally distributed.

Necessary adjustment in the model will be made for possible heteroscedasticity of variances through Kenward Roger approximation of degrees of freedom.

The model will include treatment, period, treatment sequence, and first-order carryover effect (where applicable) as fixed effects, and the baseline (predose) measurement as a covariate (where applicable).

If the variance among treatments is homogeneous, subject will be considered a random effect; if the variance among treatments is heterogeneous, the default variance components (VC) variance structure block will be used for each subject. Treatments for each PD endpoint will be tested for homogeneity of variance using the SAS procedure

After it is determined if the treatment variance is homogeneous or heterogeneous, the residuals from each mixed-effect model will be investigated for normality using the Shapiro-Wilk W test. The null and alternative hypotheses for this analysis are shown below:

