#### 7.4.1 Test Hypotheses for Primary Endpoint, Drug Liking VAS $E_{max}$

The primary objective of a HAP study is to provide information on the relative abuse potential of a test drug in humans. The statistical analysis of a HAP study should address the following questions:

1. Does the known drug of abuse (positive control) produce reliable abuse-related responses compared to placebo (study validity)?
2. Does the test drug produce abuse-related responses that are smaller than those of the positive control?
3. Does the test drug produce abuse-related responses that are similar to placebo?

To address these issues, the following hypotheses will be tested for Drug Liking VAS  $E_{max}$  at a significance level of 0.05; 2-sided 90% confidence intervals will be used.

These hypotheses will be applied to the primary endpoint, Drug Liking VAS  $E_{max}$ .

Although a margin of 15 has been selected for Hypothesis 1 to ensure consistency with the qualification phase criteria, subjects are expected to provide lower responses in the treatment phase as compared to the qualification phase. Therefore, if the difference between the positive control and placebo does not meet the recommended criterion for validity (i.e.,  $\delta_1 = 15$ ), a secondary planned analysis will be performed (refer to Section 7.4.4 for more details). A margin of 11 points is considered appropriate for Hypothesis 3 based on an analysis of Drug Liking VAS  $E_{max}$  data.

For study validity purposes, the primary endpoint,  $E_{max}$  for Drug Liking VAS, will be compared between the positive control (alprazolam 2 mg) and placebo. The comparison will assess the null hypothesis that the mean difference in Drug Liking  $E_{max}$  between alprazolam and placebo is less than or equal to 15 against the alternative hypothesis that the mean difference in Drug Liking  $E_{max}$  between alprazolam and placebo is greater than 15. If statistically significant, it will confirm the sensitivity of the study and allow for the comparison of the other pairwise comparisons shown below. The hypotheses can be expressed as follows:

where  $\mu_C$  is the mean for the positive control, alprazolam, and  $\mu_P$  is the mean for placebo, and will be applied to the following contrast:

—

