## **10.4 Methods for Handling Missing Data**

No imputation of missing PD or PK data will be performed.

The occurrence of missing PD data will be minimized by only including subjects who are rousable, and complete PD assessments in the qualification phase. In addition, all reasonable attempts will be made to rouse subjects for completion of the PD assessments in both the

qualification and treatment phases. Missing PD assessments, including reasons for the missing data, will be listed by subject, and examined on a case-by-case basis to determine if these affect subject allocation (i.e., inclusion in the Modified Completer population). If for a given PD measure, the predose value is missing, calculation of CFBmin and TA\_AOE will not be possible, and the subject will not be included in the Modified Completer population for that PD endpoint. If the actual date and/or time of a postdose PD assessment is unknown, but there is a result at that time point, the value will be used in descriptive statistics of treatment by time point summaries, and PD endpoint by treatment summaries but will be excluded from calculation of TA\_AUE and TA\_AOE which need actual time from dose in order to be calculated.

If the actual collection time of a postdose PK sample is unknown, but a valid concentration value has been measured, the sample will be set to missing in the PK analysis and will be presented in listing but excluded from descriptive statistics. Unknown baseline collection times will be handled on a case-by-case basis.

Further details on handling of missing values will be provided in the Subject Allocation and Request to Break the Blind Form.

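### Every Drug Liking test, including the validity gate, is specified only after exclusions that select on the tested contrast; the defined Completer population should be analysed alongside

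*Protocol*

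**What the plan says.** Protocol 8.1.2.3 (SAP 4.2.3) defines the Completer population: subjects who finish all five periods with sufficient Drug Liking data, judged in a blinded review before database lock. Protocol 8.1.2.4 (SAP 4.2.4) then derives the Modified Completer population by "excluding problematic subjects with unreliable responses which can alter study results". Two criteria apply to Drug Liking Emax:

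- **Criterion a:** all treatments, placebo included, lie within 5 points of each other.
- **Criterion b:** placebo Emax exceeds 60 **and** placebo minus positive control is at least 5. Both conditions are needed.

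Protocol 8.5.1 states that "all PD data will be analyzed using the Modified Completer population". SAP 7.4 repeats it: "The primary analysis of PD data will be analyzed for the Modified Completer population". This covers the validity test H1 in SAP 7.4.1, whose null is that the mean alprazolam-minus-placebo difference "is less than or equal to 15 against the alternative hypothesis that the mean difference" exceeds 15. A significant H1 opens the other comparisons. The visible text specifies no PD analysis in the Completer population, and the list of changes in SAP 12 adds none.

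Qualification (protocol 4.3) requires a placebo peak of 40 to 60 and an alprazolam peak at least 15 points higher. Protocol 8.5.2.2 nevertheless anticipates that "subjects may have lower responses with alprazolam and higher responses with placebo in the Treatment phase".

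**The concern.** H1 asks whether alprazolam beats placebo by more than 15 points. Criterion b uses that same within-subject difference to decide who is analysed, and it cuts only the lower tail. Criterion a removes differences between -5 and +5, which also lie below 15. Both exclusions therefore raise the mean that H1 tests.

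A subject who qualified and later rates placebo above 60 and above alprazolam may be answering carelessly. That subject may also be evidence that the assay does not separate the two treatments in this setting, which is what H1 is there to detect. With results from one set only, a reader could not tell whether the validity claim depends on the exclusions, and all further comparisons rest on that claim.

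**Working it through.** **1. The plan's own figure.** Inputs from protocol 8.9: mean difference 26.3, SD 18.62, margin 15, correlation 0; "an upper-tailed test with a significance level of 0.05 results in 48 completers". Power is not stated. A one-sample noncentral t calculation with SD × √2 (18.62 × 1.414 = 26.3) and effect 26.3 − 15 = 11.3 gives n = 48 at power 0.9006. The 3.0 mg inputs (26.6, 17.83) give 42 at 0.9009. So 48 and 42 are reproduced at 90% power. If 18.62 is taken as the SD of the paired difference, as the text describes it, 48 completers give power 0.994.

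**2. What one exclusion does.** Removing k of n subjects whose average difference is d, from a set with mean 15, raises the mean by k(15 − d)/(n − k). With n = 48 and k = 1, the smallest possible shift under criterion b (d = −5) is 20/47 = 0.43 points. At d = −20 it is 35/47 = 0.74. The standard error is 18.62/√48 = 2.69. One exclusion therefore moves the mean by about 0.16 to 0.28 standard errors, always upward.

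**3. H1 error at the boundary.** Simulation with a true completer difference of 15, 48 completers and a one-sided 5% paired t-test. Assumptions, none of them given in the documents: most placebo peaks lie at 50 plus a small excess capped at 10 points; a stated share lies uniformly between 62 and 90; alprazolam has SD 17, clipped to 0-100. The last two columns let alprazolam rise with the placebo elevation in the same subject. The dropped share and retained mean refer to the independent case.

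| Placebo Emax > 60 | Dropped by b | Retained mean | H1 error: independent | half shared | fully shared |
|---|---|---|---|---|---|
| 5% | 2.7% | 16.0 | 11% | 7% | 6% |
| 10% | 5.2% | 17.0 | 20% | 10% | 7% |
| 25% | 11.2% | 19.3 | 53% | 23% | 10% |

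On all completers the error is about 5% throughout. A repeat run agreed to within about one percentage point.

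**4. A second model.** Bounded scores, difference SD 18.62, alprazolam independent of placebo. With 0, 5, 10, 20 and 30% of subjects above 60 on placebo, H1 error after criterion b is 0.037, 0.091, 0.170, 0.394 and 0.603. On all completers it is 0.037 to 0.054. At 0% criterion b changes nothing.

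**5. Criterion a.** In the second model, 10% flat responders and no placebo peak above 60 give H1 error 0.123 after both criteria. With 10% of each kind it is 0.344.

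**6. The other hypotheses** (second model, criterion b, 5 to 30% above 60). H2 error at its boundary is 0.063 to 0.137. H3 error falls from 0.049-0.063 without exclusion to 0.042-0.005, so H3 becomes conservative.

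**7. At the planned effect.** With a true difference of 26.3 in the step 3 model, H1 passes in over 99% of trials with or without criterion b.

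**The case against.** The rule is prespecified and narrow. It needs placebo above 60 as well as the reversal: a subject with placebo 58 and alprazolam 50 stays in. A reader might infer that everyone who prefers placebo by 5 points, or everyone who counts against H1, is removed. The documents do not say that. Differences above −5 and up to 15 also count against H1, and criterion b never touches them. Qualification further limits criterion b to subjects who reverse a response they gave shortly before. The narrowness stands, but it does not make the selection neutral.

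The largest error rates need independent ratings. The correlation of 0 in protocol 8.9 is a sample-size input, not evidence about Treatment-phase ratings. A subject who rates everything high is seldom caught by criterion b, and the inflation then shrinks to a few points. This stands, and is why a range is given. The error is also measured against the full Completer population, which is not the population that the plan chose for its test.

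A reader might infer that the Completer set is never used. SAP 5.1.2 summarises exclusions from each population, SAP 6.2 gives demographics by population, SAP 7 opens with an exception for analyses specified otherwise, and the SAP table index is not visible. Only the absence of a specified PD analysis is supported.

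A reader might also take SAP 10.4, where missing assessments are "examined on a case-by-case basis to determine if these affect subject allocation (i.e., inclusion in the Modified Completer population"), as open discretion over the set. Sufficiency for the primary endpoint is judged blinded before lock, and the same section fixes a rule for missing predose values. Letting only criteria a and b remove subjects would contradict that rule.

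**Conclusion.** The point holds as a gap in the planned reporting. Every PD test in the visible text, the validity gate included, is run only after exclusions that act in one direction on the H1 contrast, and no PD result on the unselected completers is specified. The direction is certain whenever a subject meets criterion b: H1 is favoured. H2 is mildly favoured and H3 made conservative in the model examined, so a general bias in the test drug's favour is not supported.

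The size is uncertain. With 5-25% of subjects above 60 on placebo, H1 error at the boundary is about 11-53% under independence, 7-23% with half the elevation shared and 6-10% with all of it shared; from criterion b it is nominal if no placebo peak exceeds 60. The upper figures should not be read as the trial's error rate, because the documents give neither the share of high placebo ratings nor the correlation. If alprazolam performs near the planned 26.3, the choice of set will hardly matter to H1. It matters if the true difference is close to 15, a shift towards which protocol 8.5.2.2 itself points.

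**What to change.** Keep the Modified Completer population as primary. In SAP 7.4:

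1. Prespecify the same H1-H3 analyses of Drug Liking Emax on the Completer population as a sensitivity analysis, reported side by side with the primary results.
2. Report the number of subjects excluded under criterion a and under criterion b.
3. State that a validity conclusion that holds only after the exclusions will be described as such.

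SAP 10.4 can stay as it is. The cost is a short SAP revision and one repeated set of tables on data already held. The downside is that the two sets may disagree, and the report would then have to say so. If few subjects meet the criteria, the results should agree and the validity claim gains support.
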